3.5.3. Premature Study Termination

The Sponsor reserves the right to discontinue the study for any safety, ethical or administrative reason at any time.

3.6. Investigational Drug Product and Accountability

3.6.1. INVESTIGATIONAL DRUG PRODUCT

VM202 is a DNA plasmid containing a novel genomic cDNA hybrid human hepatocyte growth factor (HGF) coding sequence (HGF) expressing two isoforms of HGF, The key feature of HGF is that it was designed by inserting a series of intron sequences into certain sites of HGF cDNA so that both isoforms of HGF protein are expressed simultaneously and efficiently as in the human genome. Because there is no change in the coding region of the HGF gene, HGF proteins generated from VM202 are identical to the wild-type human HGF proteins.

The plasmid has	ba	se pairs, a	enhancer /	pron	noter, a gro	owth l	ormone
	terminato	or sequence	originator,	, and			
resistance gene,	on a	backbone.		·			

VM202 is supplied in a sterile glass vial containing study product. VM202 should be stored in a refrigerator at temperatures between 2°C and 8°C in an appropriately locked room accessible only to the pharmacist, or a duly designated person. Since VM202 does not contain preservatives, opened vials of VM202 and VM202 reconstituted with WFI must be used within 12 hours. A complete description of test article administration can be found in Appendix 7.

3.6.2. PLACEBO

The placebo will be sterile VM202 vehicle. Components of VM202 vehicle are provided in Table 5. VM202 excipients are supplied in a sterile glass vial in liquid form. Each vial is only to be used for one subject. Visually, VM202 vehicle is indistinguishable from reconstituted VM202.

Table 5. Components of VM202 Vehicle

COMPONENT	Function	COMPOSITION	

3.6.3. PRODUCT ACCOUNTABILITY

In accordance with federal regulations (21CFR 312.62), all Investigators or his/her designee are required to keep accurate records showing final disposition of all investigational drugs.

Investigational drugs are to be used only in accordance with this protocol and under supervision of the Study Pharmacist or a duly designated person. The Study Pharmacist or his/her designee will maintain an accurate record of the receipt of the VM202 and placebo as shipped by the Sponsor/Designee, including the date received. In addition, an accurate study drug disposition record will be kept, specifying the date and amount dispensed to each subject. This inventory record must be available for inspection at any time by the unblinded CRO representative. Copies of these records will be provided to the Sponsor by the Study Pharmacist at the conclusion of the study.

After the study is completed, the Study Pharmacist must account for all study drug used, unused and partially used. Unused study medication from the study site will be returned to the Sponsor/Designee as directed in writing by the Sponsor for gross reconciliation.

3.6.4. Dose and Administration

VM202 is supplied in a sterile glass vial containing study product. Before administration, it will be reconstituted with study pharmacist for a final VM202 concentration of 0.5 mg / mL. Each reconstituted vial is only to be used for one subject. The VM202 arm will receive only VM202 injections. The placebo group will receive only VM202 vehicle injections. All subjects will receive 16 injections in ipsilateral calf of the affected foot with the target ulcer at each injection visit (Days 0, 14, 28 and 42). A complete description of test article administration can be found in Appendix 7.

3.7. PRIOR AND CONCOMITANT MEDICATION

All concomitant medications (taken within 60 days of the first injection) will be recorded at each study visit. For each medication taken, the following information will be collected:

- Medication trade name:
- Indication for which the medication was given;
- Dose/strength, route, and frequency of administration;
- Date started and date stopped (or continuation at study exit).

4. EXAMINATIONS AND EVALUATIONS

4.1. EVALUATIONS CONDUCTED AT BASELINE ONLY

4.1.1. MEDICAL HISTORY

A relevant medical history will be obtained at Baseline. All positive and negative findings will be carefully documented on the study worksheets. A new finding discovered during the Screening/Baseline evaluation and prior to the first study drug administration (Day 0) will be considered to be part of the medical history and will not be recorded as an adverse event.

The Investigator will perform an especially detailed assessment of past diabetes and PAD history to include all events and interventions prior to study enrollment. Care should be taken to exclude ulcers due vasculitis, pyoderma gangrenosum, necrobiosis lipoidica, hydrostatic pressure/venous insufficiency, any neoplasms (basalioma, Kaposi's sarcoma, squamous cell carcinoma etc.), or a burn.

4.1.2. PHYSICAL EXAM

A physical exam will be performed at Screening. The exam will include the following: head, eyes, ears, nose, and throat (HEENT), heart, lungs, abdomen, extremities, lymph nodes, musculoskeletal, neurological, and gastrointestinal systems. Any abnormalities should be categorized as clinically significant (CS) or not clinically significant (NCS), and the abnormalities should be recorded in the subject's study worksheets. Actual height will be measured.

4.1.3. CANCER SCREENING

All subjects participating in this trial must undergo routine cancer screening. The history and diagnosis of potential or apparent malignant and non-malignant diseases and neoplasms will be assessed through several diagnostic tests and procedures. Some diagnostic tests and procedures performed prior to study consent and documented in the subject's medical history may be acceptable where noted. Routine cancer screening includes the following:

- 1. Cervical Cancer Screening Papanicolaou (PAP) smear
 - Women < 21 years no screening required
 - Women that have undergone a complete hysterectomy no screening required
 - Women between the ages of 21 and 65 (inclusive), testing within the last 3 years
 - Women > 65 years old with regular screening within the last 10 years with normal results no screening required. Any abnormal finding in the past 10 years requires screening at study entry.
- 2. Breast Cancer Screening (women only) mammogram
 - Women between the ages of 45 and 54 (inclusive) normal findings within one year
 - Women ≥ 55 normal findings within 2 years
- 3. Lung Cancer Screening For subjects ≥ 55 years and ≤ 74 years: low dose chest CT scan (LDCT w/o contrast) conducted within 3 months prior to signing the informed consent form IF the subject has a ≥ 30 pack year smoking history AND is still smoking or quit within the last 15 years. If results are not available, screening needs to be performed.

A pack year is number of cigarette packs smoked per day multiplied by the number of years the subject has smoked (e.g., someone who smoked a pack of cigarettes per day for 30 years has a 30 pack-year smoking history, as does someone who smoked 2 packs a day for 15 years).

4. Colon Cancer - For subjects ≥ 50 years: fecal occult blood test. A positive fecal occult blood test requires follow-up testing which is beyond the scope of this study. If follow-up testing rules out cancer, the subject will be able to participate in the study if the subject is still interested.

Subjects with a medical history or family history of colon cancer in any first-degree relative must have documentation of a negative colonoscopy performed within the past 12 months.

4.1.4. VIRAL SCREENING

The local laboratory will be responsible for Screening viral testing and assays to include: HIV-1, HIV-2, HTLV, Hepatitis B surface antibody (HBsAb), Hepatitis B core antibody (IgG and IgM; HBcAb), Hepatitis B surface antigen (HBsAg) and Hepatitis C antibodies (Anti-HCV).

4.1.5. FOOT X-RAY

X-rays of the target foot will be taken in two projections: dorsal-plantar (DP) and oblique. These can be done under weight bearing or non-weight bearing conditions, at the investigator's discretion.

4.1.6. 12-LEAD EKG

A 12-lead electrocardiogram (EKG) will be conducted at Screening. The EKG recording will be printed out, and a copy will be placed with subject records. Any (clinically significant) abnormalities will be reported.

4.1.7. Pregnancy Test (women of childbearing potential only)

For women of childbearing potential, a urine beta human chorionic gonadotropin (β-HCG) test will be performed at Screening. Results of the test must be negative and effective contraception documented. Acceptable methods of contraception include:

- Barrier type devices (e.g., female condom, diaphragm and contraceptive sponge) used only in combination with a spermicide;
- Intrauterine device;
- Oral contraceptive agents;
- Depo-provera (medroxyprogesterone acetate);
- Levonorgestrel implants;

Abstention, the rhythm method, or contraception by a partner are not considered acceptable methods of contraception.

4.2. EVALUATIONS CONDUCTED THROUGHOUT THE STUDY

4.2.1. DOCUMENTATION OF TARGET ULCER

At each visit at which the target ulcer is present, a photograph of the ulcer will be taken before and after debridement. Measurements of the surface area, depth, perimeter and volume of the target ulcer will be performed. Instructions can be found in Appendix 5.

4.2.2. RETINAL FUNDOSCOPY

Proliferative retinopathy, defined as the presence of new proliferating blood vessels (neovascularization) arising from the retina or optic disc and growing on the retinal surface or into the vitreous cavity, will be assessed by retinal fundoscopy at Screening for eligibility and repeated at Day 210. Retinal fundoscopy must be performed by an ophthalmologist within 3 months of Screening.

In cases where fundoscopy alone is deemed insufficient to determine eligibility, fluorescein angiography may be conducted at Screening.

4.2.3. CONCOMITANT MEDICATIONS

Concomitant medications will be recorded at each visit using the trade name or generic name as described in Section 3.7.

4.2.4. VITAL SIGNS

Vital signs consisting of blood pressure (while subject is sitting), temperature, weight, heart rate, and respiratory rate will be measured and recorded at Screening and at every study visit through the 7-month follow-up. Weight will not be measured during Wound Assessment and Dressing Change or Confirmation of Wound Closure visits.

4.2.5. SERUM CHEMISTRY, HEMATOLOGY AND HBA1C

Evaluation of serum chemistry and hematology will be conducted at Screening, Day 0, Day 42, Day 90, Day 120 (4 months) and Day 210 (7 months). Evaluations will be conducted by a local laboratory at each site.

Serum chemistry evaluations will include: calcium, glucose, sodium, potassium, chloride, bicarbonate, blood urea nitrogen (BUN), creatinine, eGFR (at Screening only), alanine aminotransferase (ALT), aspartate aminotransferase (AST), total bilirubin, alkaline phosphatase, albumin, and total protein.

Hematology evaluations will include: complete blood count (CBC): red blood cells (RBC); hemoglobin (Hgb), hematocrit (HCT), platelets and white blood cells (WBC) with differential. Abnormal readings do not necessarily constitute an adverse event; the results need to be reviewed in the context of the subject's health.

HbA1c will be determined at Screening, Day 0, Day 120 (4 months) and Day 210 (7 months) at a local laboratory at each site. Laboratory testing by visit is provided in Appendix 1.

4.2.6. SERUM HGF

HGF serum levels will be determined immediately pre-treatment on Day 0, immediately pre-treatment on Day 28, Day 60, and Day 90.

A minimum 6 cc blood draw will be taken at each time point. Allow blood to clot for 30-60 minutes at room temperature then centrifuge for 10 minutes at 1000 x g. Divide the isolated serum into six (6) equal aliquots of ~ 0.3 mL each. (0.5-mL plastic storage tubes provided). Samples should be labeled with study number, subject ID, draw date and time, and visit interval (i.e., Day 0, Day 28, Day 60 or 90). Samples will be maintained in a cooler containing dry ice and then placed in a \leq -65°C freezer until shipped for analysis.

At the request of the Sponsor or its designee, serum HGF samples will be batched with VM202 samples and shipped in a special container with temperature tracking recorder to for analysis.

Note, will provide collection tubes, plastic vials, labels, shipment materials including temperature tracking devices to each participating site for use during the study.

4.2.7. COPIES OF VM202 IN WHOLE BLOOD

The number of copies of VM202 in whole blood will be determined by PCR at Day 0 (pre-injection, and 2 hours $[\pm 1 \text{ hour}]$ post injection), at Day 14 (pre-injection, and 2 hours $[\pm 1 \text{ hour}]$ post injection), Day 28 (pre-injection, and 2 hours $[\pm 1 \text{ hour}]$ post injection), Day 42 (pre-injection, and 2 hours $[\pm 1 \text{ hour}]$ post injection), Day 60, and Day 90.

Six (6) cc of whole blood will be collected in EDTA-coated tubes, inverted >5 times and transferred to plastic sterile and or RNase and DNase free vials of ~0.6 − 1 cc aliquots each for a total of 5 aliquots per time point. These will be maintained in a ≤ --65°C freezer until shipped for analysis. Samples should be labeled with study number, subject ID, draw date and time, and visit interval (i.e., Day 0 pre, Day 0 post, Day 14 pre, Day 14 post, Day 28 pre, Day 28 post, Day 42 pre, Day 42 post, Day 60, and Day 90).

At the request of the Sponsor or its designee, VM202 samples will be batched with serum HGF samples and shipped in a special container with temperature tracking recorder to analysis.

Note, will provide collection tubes, plastic vials, labels, shipment materials including temperature tracking devices to each participating site for use during the study.

4.2.8. ANKLE BRACHIAL INDEX (ABI), TOE BRACHIAL INDEX (TBI) AND TOE PRESSURE IN THE TARGET LIMB

Ankle-Brachial Index (ABI) and Toe Brachial Index (TBI) will be determined in the target limb at Screening, before the first treatment (injection) on Day 0, Day 120 (4 months) and Day 210 (7 months). Toe pressure will be determined at Screening in the target limb. Instructions can be found in Appendix 6.

4.2.9. Transcutaneous Oxygen Pressure (TcPO₂)

Transcutaneous oxygen pressure (TcPO₂) will be measured before the first treatment (injection) on Day 0, Day 120, and Day 210 Visits as a sub-study at 3 -10 sites. TcPO₂ measurement sites will include the anterior and posterior calf and dorsum of the foot. Because TcPO₂ measurements are instrument dependent, investigators should use the same instrument for all TcPO₂ assessments and follow the standard

procedures defined by their instrument's manufacturer. If a sensor placement site is unavailable due to amputation or areas of ulceration/gangrene, sensor placement site will be assigned a clinically equivalent default TcPO₂ value of zero pressure ("0 mmHg"). Hard copy instrumentation printout will be included in the source documentation to support the TcPO₂ data. The limb/chest TcPO₂ index will be calculated by using the lesser of the lower limb measurements.

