The target ulcer will be documented at screening visit before and after debridement. This includes photograph, surface area, depth, perimeter and volume measurements. Subjects will come in once a week for dressing changes and for wound evaluation during screening.

If applicable, the subject will be washed out of prohibited medications prior to Day 0 injections. During washout, screening procedures may be performed. At Day 0, the target ulcer will be documented by photograph, surface area measurement, depth, perimeter and volume. Subjects must have a nonhealing ulcer on Day 0 that meets study entry inclusion criterion #5 and exclusion criterion #4 to be eligible for study participation.

Patients will receive IM injections in the ipsilateral calf of the affected foot of either VM202 or placebo on Day 0, Day 14, Day 28 and Day 42 as follows:

Treatment: Days 0, 14, 28, 42

TREATMENT]	Dose VM20	FINAL DOSE		
GROUP	DAY 0	DAY 14	DAY 28	DAY 42	VM202 (mg)
VM202	4	4	4	4	16
Placebo	0	0	0	0	0

0 indicates injections of Placebo

VM202 will be delivered in a solution of 0.5 mg VM202 / mL. All subjects will receive sixteen (16) 0.5-mL injections of VM202 or placebo at each injection visit as follows:

Subjects in the *VM202 Treatment Arm* will receive the following IM injections in the calf of the leg with the target ulcer:

- Day 0 16 injections of 0.5 mL of VM202 (4 mg of VM202)
- Day 14 16 injections of 0.5 mL of VM202 (4 mg of VM202)
- Day 28 16 injections of 0.5 mL of VM202 (4 mg of VM202
- Day 42 16 injections of 0.5 mL of VM202 (4 mg of VM202)

Subjects in the *Placebo Group* will receive 16 injections of 0.5 mL VM202 vehicle in the ipsilateral calf of the affected foot with the target ulcer at each injection visit.

Note: Visually, placebo is indistinguishable from reconstituted VM202. The subject and clinician will not be able to distinguish placebo from VM202 injections.

Subjects will continue to come to the clinic once a week for dressing changes and wound assessment until the ulcer has healed or study exit, whichever comes first.

HGF serum levels will be determined immediately pre-treatment on Day 0, immediately pre-treatment on Day 28, and on Day 60 and Day 90.

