4.2. Other Efficacy Endpoints

- Time to complete wound closure of foot ulcer
- Proportion of subjects with a target wound closure by 7 months
- Percent change in wound volume at 2 months (Day 60), 2.5 months (Day 74), 3 months (Day 90), 4 months (Day 120), and 7 months (Day 210)
- Percent change in wound perimeter, area and wound depth at 2 months, 2.5 months, 3 months, 4 months, and 7 months
- Proportion of subjects with formation of new ulcers on the target foot by 2 months, 2.5 months, 3 months, 4 months, and 7 months
- Time to major amputation in the target limb
- Time to minor amputation in the target limb
- Change in target limb ABI at 4 months and 7 months
- Change in target limb TBI at 4 months and 7 months
- Change in TcPO₂ at 4 months and 7 months
- Change in the overall quality of life and each domain score (well-being, physical symptoms and daily living, social life) of CWIQ from Day 0 at 4 months and 7 months

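### The 0 mmHg default for an ulcerated TcPO₂ sensor site can make closure of a dorsal foot ulcer look like a gain in oxygenation

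*Protocol*

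**What the plan says.** Protocol section 4.2.9 describes the measurement. The TcPO₂ "measurement sites will include the anterior and posterior calf and dorsum of the foot", and readings are taken "on Day 0, Day 120, and Day 210 Visits as a sub-study at 3 -10 sites". The rule for a sensor site that cannot be used is "unavailable due to amputation or areas of ulceration/gangrene, sensor placement site will be assigned a clinically equivalent default", with the default set at 0 mmHg. The limb/chest index is formed "by using the lesser of the lower limb measurements".

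Three other places bear on this rule:

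- Protocol synopsis, study procedures: "Subjects must have a nonhealing ulcer on Day 0 that meets study entry inclusion criterion #5". Every subject therefore has an open foot ulcer when baseline TcPO₂ is taken.
- SAP section 4.5: the dorsum of the foot is one of the ten wound locations originally listed, before they were regrouped as weight-bearing or not.
- SAP section 4.2: "Change in TcPO₂ at 4 months and 7 months" is among the other efficacy endpoints, which SAP section 8.4 classes as exploratory.

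SAP section 9.4.4 moves from ABI and TBI (9.4.4.8 and 9.4.4.9) to the wound questionnaire (9.4.4.10) and has no subsection for TcPO₂. Nothing says whether the endpoint is the site value or the index, or how the assigned zeros are handled.

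**The concern.** One place on the foot can be both a sensor site and the ulcer being treated. When it is, the baseline reading is a convention and not a measurement, and the minimum rule carries that convention into the whole-limb index. Once the ulcer closes, a real reading replaces the zero. A baseline of 0 cannot fall, so the change can only be zero or positive, whatever happens to perfusion.

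Because closure is the outcome the drug is meant to improve, affected subjects would show a TcPO₂ difference in favour of the arm that heals more, even with identical oxygenation. A reported TcPO₂ gain could then not be separated from closure in those subjects. The rule also works in reverse: a new ulcer, gangrene or an amputation at a sensor site after baseline appears as a fall to 0.

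**Working it through.** The documents give no TcPO₂ reading, variance, power or sample size, so there is no stated figure to reproduce. The check applies the rule in Protocol section 4.2.9 while holding every true value constant.

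**Inputs from the documents**
- Index = min(anterior calf, posterior calf, dorsum) / chest, with an ulcerated site set to 0 (Protocol 4.2.9).
- Assumed closure by 4 months: 50% to 60% on VM202 and 20% to 30% on placebo (SAP section 6). The smallest gap is 50% vs 30% and the largest 60% vs 20%.
- Gangrene is excluded at entry (Protocol 3.3.2, criterion 6), so a baseline zero comes from ulceration or an earlier amputation.

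**Assumed inputs**
- True calf values 55 and 50 mmHg, chest 60 mmHg.
- True dorsum value T = 20 to 40 mmHg, the lowest of the three sites and unchanged over time.
- f, the share of sub-study subjects whose ulcer makes the dorsum site unavailable on Day 0: 5% to 30%.
- Affected subjects close at the plan's rates, closed ulcers are still closed at the Day 120 visit, and unclosed ones still score 0.

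**One affected subject**
- Day 0: min(55, 50, 0)/60 = 0.
- After closure: 20/60 = 0.33, 30/60 = 0.50 or 40/60 = 0.67.
- Apparent gain: 20, 30 or 40 mmHg, with a true change of 0.

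**One subject with an ulcer elsewhere, such as the sole (T = 30)**
- Before and after: min(55, 50, 30)/60 = 0.50. There is no artefact.

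**Between arms**

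Expected artefact = f × (p_t − p_c) × T, where p_t and p_c are the closure rates.

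| | 50% vs 30% | 60% vs 20% |
|---|---|---|
| Affected subjects only (f = 1), T = 20 to 40 | 0.20 × 20 = 4 to 0.20 × 40 = 8 mmHg | 0.40 × 20 = 8 to 0.40 × 40 = 16 mmHg |
| Whole sub-study, f = 5% (T = 20) to 30% (T = 40) | 0.05 × 4 = 0.2 to 0.30 × 8 = 2.4 mmHg | 0.05 × 8 = 0.4 to 0.30 × 16 = 4.8 mmHg |

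The same artefact arises whether the endpoint is the dorsum value or the index numerator.

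**Two possible repairs, with T = 30**
- Drop the zeros but keep the lowest available site: baseline is min(55, 50) = 50 and follow-up is min(55, 50, 30) = 30. Healing now shows as a loss of 20 mmHg.
- Keep the site set fixed at what was measurable on Day 0: min(55, 50) = 50 at both visits, so the change is 0, as it should be.

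**The case against.** The strongest counter-argument is about scope. A reader might infer that any ulcer healing, or any healing difference between arms, produces a TcPO₂ difference. The documents do not support that. Two of the three sensor sites are on the calf, where a target foot ulcer cannot lie. The dorsum is one of ten listed wound locations. With ulcers of 0.5 to 15 cm² at entry, even a dorsal ulcer need not make the sensor site unusable. This objection stands and limits the point to the affected subset.

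A reader might also infer that TcPO₂ is meant to show a perfusion effect separate from closure. Neither document states that purpose, so the point does not rest on it.

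Nor does the rule bias a specified test, because the SAP specifies none for TcPO₂ change. That is a gap in its own right, and it is where the repair belongs.

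The practical stakes are small. SAP section 1 reports 7 + 5 + 16 + 16 = 44 subjects enrolled, and section 10 records early stopping. With equal enrolment over 30 study centres (an assumption), 3 to 10 centres would supply about 44 × 3/30 = 4.4 to 44 × 10/30 = 14.7 subjects over both arms. Small numbers also make each swing matter, however. In an assumed arm of 10, one change from 0 to 30 mmHg moves the mean by 3 mmHg; in an arm of 5, by 6 mmHg.

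Finally, the zero default is prespecified and does useful work for limbs that deteriorate. Restricting the analysis to sites measured at both visits would drop those lost after baseline to amputation, gangrene or new ulceration. That is missingness that depends on outcome and removes the worst limbs. This also stands, and it determines the form of the fix.

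**Conclusion.** The point holds for a subset. Where an ulcer makes the dorsum site unavailable on Day 0, the zero default and the minimum rule together turn closure into an apparent TcPO₂ gain with no true change, and neither document corrects for it. The size ranges above depend on the assumed dorsum values, the assumed share affected and the plan's closure rates applying to affected subjects. The direction depends only on one arm healing more. The share affected could be higher or lower than assumed. Since protocol version G dropped the exclusion for more than one ulcer on the target foot (SAP section 1), a non-target ulcer could also trigger the rule.

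This is a minor point about an exploratory sub-study endpoint, worth correcting because the repair uses data already being collected. It does not touch the primary endpoint, which rests on closure alone.

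**What to change.** Add a TcPO₂ subsection to SAP section 9.4.4 that does the following:

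1. State whether the endpoint is the site value or the limb/chest index.
2. Compute change, including the minimum used in the index, over one fixed set of sensor sites per subject: those actually measurable at baseline. Treat a site unavailable at baseline because of ulceration or amputation as not measurable at every visit.
3. Report, by arm and visit, the sensor sites lost after baseline to amputation, gangrene or new ulceration. Show results with those sites set to 0 and again with them treated as missing. In the missing version the index at that visit should be missing too, since a minimum over fewer sites no longer compares like with like.
4. Keep the protocol's full zero-default version as a sensitivity analysis.

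There is a precedent in SAP section 9.4.4.9, which omits TBI results when the toe-pressure method differs between a subject's assessments. The cost is SAP wording, fewer evaluable sensor sites in an already small sub-study, and a little more analysis. No new data are needed.
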